2.1.2 Prior, concomitant or post treatment medications (other than anticancer therapies)

All medications taken within 21 days before the first study treatment administration and at any time during the study treatment period are to be reported in the case report form pages.

All medications will be coded using the World Health Organization-Drug Dictionary (WHO-DD) using the version currently in effect at Sanofi at the time of database locks.

- Prior medications are those the patient used prior (within 21 days) to first IMP intake. Prior medications can be discontinued before first administration or can be ongoing during treatment phase.
- Concomitant medications are any treatments received by the patient concomitantly to the IMP(s), from first administration to the last treatment infusion +30 days. A given medication can be classified both as a prior medication and as a concomitant medication. Concomitant medications do not include medications started during the post treatment period (as defined in the observation period in [Section 2.1.4](#)).
- Post treatment medications are those the patient took in the period running from 30 days after the last treatment infusion up to the end of the study.

Premedications

As defined in Section 8.2.2 of the study protocol, patients will routinely receive premedications prior to SAR566685 infusion to reduce the risk and severity of infusion-related hypersensitivity reactions and corneal toxicities. Premedications are defined in the protocol as non-investigational medicinal product(s). The recommended premedication agents are:

- For hypersensitivity reactions:

Premedication with histamine H1 antagonist (diphenhydramine 50 mg given orally approximately 1 hour before SAR566658 administration) is required for all patients

- For corneal toxicity:

Topical artificial tears and /or hyaluronic ophthalmic gel, vasoconstrictor such as neosynephrine (or equivalent), corticosteroid ocular gel such as Sterdex or dexamethasone 0.16%.

The use of cold eye mask/pad (unless patient cannot tolerate it) from start until end of infusion

Any technical details related to computation, dates, imputation for missing dates are described in [Section 2.5](#).

2.1.3 Efficacy endpoints

2.1.3.1 Primary efficacy endpoint(s)

The primary efficacy endpoint will be the Overall Response Rate (ORR) defined as the proportion of patients with confirmed complete response (CR) or confirmed partial response (PR) as Best

Overall Response (BOR), assessed by the Investigator (based on RECIST 1.1), relative to the total number of patients in the efficacy population (see [Section 2.3.1](#)). Confirmation of objective responses will be performed by repeat tumor imaging (Computed Tomography [CT] scan, MRI) at least 4 weeks after the first radiological documentation of response.

Tumor assessments will be performed every 6 weeks (ie, every 2 cycles) during the treatment period and every 6 weeks during the follow-up period if a patient discontinues treatment prior to radiologic disease progression.

Tumor assessments after the initiation of post-treatment anti-cancer therapy will be excluded from the determination of Best Overall Response in a patient. See [Appendix B](#) (Determination of tumor response) for details.

Best Overall Response

BOR is the best tumor response observed from first study treatment infusion until disease progression, death or initiation of post-treatment anti-cancer therapy, whichever occurs first.

Primary ORR analysis can be performed when all patients treated in Part 2a and Part 2b have had at least 4 postbaseline tumor assessments, experienced confirmed objective response, or have discontinued the study for any reason. However, if the primary criteria of 7 responders is either met or not met with certainty at the end of the Part 2a in the selected dose when all patients have had 2 postbaseline tumor assessments, experienced confirmed objective response, or discontinued the study for any reason and when all the patients of the Part 2b have had 2 postbaseline tumor assessments, experienced confirmed objective response, or discontinued the study for any reason, analysis may be done at that time instead.

Best tumor shrinkage

For patients with measurable disease, the best tumor shrinkage will be defined by the best relative change from baseline as follows:

$$Y = 100 \times \frac{Y_{smallest} - Y_{baseline}}{Y_{baseline}}$$

Where Y is the sum of longest diameter of the target lesions.

2.1.3.2 Secondary efficacy endpoint(s)

The secondary efficacy endpoints include duration of response (DOR), Disease Control rate (DCR), Time to progression (TTP) and Progression Free Survival (PFS).

2.1.3.2.1 Duration of response

The duration of response will be defined as the time from the date of first initial occurrence of a subsequently confirmed CR or PR to the date of first radiological documentation of disease

progression (using RECIST 1.1) before the initiation of any post-treatment anti-cancer therapy or death (due to any cause), whichever occurs first.

Duration of response is determined only for patients who have achieved a response of confirmed CR or PR.

If a patient receives post-treatment anti-cancer therapy before radiologic progression or death, the duration of response will be censored at the date of the last valid response assessment without evidence of progression performed before the initiation of the post-treatment anti-cancer therapy.

If a patient receives post-treatment anti-cancer therapy without radiologic progression or death, the duration of response will be censored at the date of the post-treatment anti-cancer therapy.

In the absence of radiologic progression, death or post-treatment anti-cancer therapy, the duration of response will be censored at the date of the last valid response assessment without evidence of progression.

A valid response assessment is defined as a response assessment with a response different of NE.

2.1.3.2.2 Disease control rate

Disease control rate is defined as the proportion of patients with confirmed CR or PR or stable disease (SD) lasting at least 3 months as assessed by the Investigator (based on RECIST 1.1) relative to the total number of patients in the relevant efficacy population (see [Section 2.3.1](#)). The calculation of the duration of stable disease is critical for the selection of patients with stable disease lasting at least 3 months. The duration of stable disease will be calculated according to the following rules:

- The duration of stable disease will be calculated as the time from the date of first study treatment infusion to the date of first documentation of progression, date of death or date of last valid tumour assessment before the initiation of any post-treatment anti-cancer therapy.
- If a patient receives post-treatment anti-cancer therapy before radiologic progression or death, the duration of response will be calculated until the date of the last valid response assessment without evidence of progression performed before the initiation of the post-treatment anti-cancer therapy.
- If a patient receives post-treatment anti-cancer therapy without radiologic progression or death, the duration of stable disease will be calculated until the date of initiation of the post-treatment anti-cancer therapy.

In the absence of disease progression, death or post-treatment anti-cancer therapy, the duration of stable disease will be calculated to the date of the last valid response assessment without evidence of progression.

A valid response assessment is defined as a response assessment with a response different of NE.

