
ENDPOINT(S)
	
Primary endpoints:
 
Part 1
 
Safety endpoint
 
Incidence of investigational medicinal product (IMP)-related predefined safety criteria during Cycle 1 and Cycle 2.
 
Predefined safety criteria are defined as the occurrence of any following related TEAE using NCI CTCAE v4.03:
 
 • Grade ≥ 3 TEAE from the System Organ Class of eye disorders. • Grade ≥ 3 peripheral neuropathy (Preferred Term). • Grade ≥ 4 TEAE. 
Efficacy endpoint
 
Objective Response Rate, defined as the proportion of CR and PR as best response according to RECIST 1.1. Confirmation of objective responses will be performed by repeat tumor imaging (Computerized Tomography [CT] scan, Magnetic Resonance Imaging [MRI]) at least 4 weeks after the first radiological documentation of response.
 
Part 2
 
Part 2a (expansion/overexpressing CA6 cohort)
 
Objective Response Rate (see Part 1).
 
A total of 15 additional patients will be treated and the analyses performed on the whole population treated at the selected dose (Part 1 and Part 2a).
 
Part 2b (mild CA6 expression cohort)
 
Objective Response Rate (see Part 1).
 
A total of 20 patients with a mild CA6-positive membrane intensity, with at least 1% positive tumor cells at intensity $\geq 1+$ and $< 30\%$ of tumor cells at intensity of 2+, 3+, will be treated and the analyses performed.
 
Secondary endpoints (Part 1 and Part 2):
 
 • Disease control rate (DCR): number of patients with CR, PR and stable disease (SD) with a duration of at least 3 months. • Duration of Response (DOR): defined as the time from the first documentation of objective tumor response (CR or PR) to the first radiological documentation of tumor progression or death (due to any cause), whichever comes first. • Progression-free survival (PFS): defined as the time interval between the date of first study treatment administration and

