9.2 SECONDARY ENDPOINTS

9.2.1 Secondary efficacy endpoints

- DCR defined as the proportion of patients with CR, PR, or SD using RECIST 1.1 lasting more than 3 months as BOR.
- DOR defined as the time from the date of the first documentation of objective tumor response (CR or PR) to the date of first radiological documentation of tumor progression using RECIST 1.1, or death (due to any cause), whichever comes first.
- PFS defined as the time interval between the date of first study treatment administration and the date of the first radiologically documented tumor progression using RECIST 1.1, or death (due to any cause), whichever comes first.
- TTP defined as the time interval from the date of first study treatment administration and the date of the first radiologically documented tumor progression using RECIST 1.1.

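### The 3-month stable-disease rule for disease control does not fit 6-weekly scans: if data are cut after two scans, stability shown at week 12 fails, while shorter documented stability can pass

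*SAP*

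**What the plan says.** **Threshold.** SAP 2.1.3.2.2 counts "stable disease (SD) lasting at least 3 months as assessed by the Investigator" alongside confirmed CR and PR. The protocol synopsis agrees ("stable disease (SD) with a duration of at least 3 months"), but Protocol 9.2.1 has "lasting more than 3 months as BOR". Neither document converts 3 months to days.

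**Duration.** SAP 2.1.3.2.2 runs SD "from the date of first study treatment infusion to the date of first documentation of progression, date of death" or, failing both, to the last valid assessment before new therapy. With no progression, death or new therapy, "the duration of stable disease will be calculated to the date of the last valid response assessment without evidence of progression".

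**Scan schedule.** SAP 2.1.3.1: "Tumor assessments will be performed every 6 weeks (ie, every 2 cycles) during the treatment period". Protocol 10.1.4 counts the 6 weeks from first administration. No window is stated for on-treatment scans.

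**When data may be cut.** The default for both analyses is at least four post-baseline assessments per patient, a confirmed response, or discontinuation. Two assessments suffice if the responder criterion is already settled with certainty (Protocol 6.2.2; SAP 2.1.3.1 and 3). SAP 4 also allows a lock after two assessments if the study stops early.

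**The concern.** A 91-day threshold combined with scans every 42 days leaves the week-12 scan one week short. The end date also depends on how follow-up ends: a progression or death date extends the SD interval beyond the last scan that showed stability, whereas ongoing follow-up does not. A patient with longer documented stability can therefore be scored as a failure while one with shorter documented stability is scored as controlled. DCR is a named secondary endpoint in both parts. Its value would depend on which permitted cut-off is used and, to a lesser extent, on whether second scans run late.

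**Working it through.** The documents state no figure for DCR under this rule, so there is none to reproduce.

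**1. Dates.** Second scan: 2 × 42 = 84 days; third: 126 days. Three months is 3 × 30.4375 = 91.3 days, or 90 days with 30-day months, or 89 to 92 calendar days. Day 84 is 84/30.4375 = 2.76 months. It fails under each of these and passes only if a month is 28 days. The first on-schedule scan that qualifies is Day 126.

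**2. Three records under the SAP text.** SD at Day 42 is a valid best response because SAP Appendix B sets the minimum at 35 days.

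| Record | SD duration | Scored |
|---|---|---|
| SD at Days 42 and 84, ongoing, no later scan | 84 days | not controlled |
| SD at Day 42, second scan late at Day 92 shows progression | 92 days | controlled |
| SD at Day 42, no further scan, death at Day 95 | 95 days | controlled |

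**3. Loss at a two-scan cut-off, no responders.** Assumptions: 20 patients (the size of Part 2b), uniform accrual over A days, scans on schedule, exponential time to progression with median m days, and cut-off when the last patient reaches Day 84.

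A patient's latest scan is week 12 if first infusion fell less than 42 days before the last patient's. With M the last patient's entry time, the expected number is 1 + 19 × 42 × E(1/M). Since E(1/M) = 20/(19A), this equals 1 + 840/A. The proportion progression-free at Day 84 is 2^(−84/m): 50% for a 12-week median and 35.4% for 8 weeks. The loss is (1 + 840/A)/20 times that proportion.

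| Accrual | A (days) | Patients with week 12 as last scan | DCR, 12-week median (50% by the week-12 scan) | DCR, 8-week median (35.4% by the week-12 scan) |
|---|---|---|---|---|
| 4 months | 121.75 | 7.90 | 30.3% (loss 19.7) | 21.4% (loss 14.0) |
| 8 months | 243.5 | 4.45 | 38.9% (loss 11.1) | 27.5% (loss 7.9) |
| 12 months | 365.25 | 3.30 | 41.8% (loss 8.2) | 29.5% (loss 5.8) |

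Simulation gave the same values to within rounding. The range is about 6 to 20 points, or 1.2 to 4.0 patients.

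**4. Allowing for responders.** Confirmed CR and PR need no minimum duration. In the first-in-human breast cohort (Protocol 4.2), 3 of 19 patients had a confirmed PR and DCR was 36.8%, that is 7/19, so 3/7 of controlled patients were responders. If that share held and all were confirmed by cut-off, only 4/7 of the loss remains: 5.8 × 4/7 = 3.3 to 19.7 × 4/7 = 11.3 points.

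**5. Default four-scan cut-off.** SD at Day 84 is followed by a Day 126 scan or a progression date of Day 126, and both exceed 91 days. Simulated DCR is the same under both rules (50% and 35%), so the loss is 0. Patients whose follow-up ends after week 12 without progression, death or new therapy are the exception.

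**6. Progression at a late second scan.** On schedule, progression at Day 84 fails, so the error is 0. For the error to arise, the second scan must be about 6 to 8 days late or more, depending on the conversion. Suppose scans follow cycles and a proportion of two-cycle blocks is delayed by 4 to 14 days (an assumption; Protocol 8.2.3.2 allows delays of up to 2 weeks). At 5%, 10% and 15% of blocks, about 1.5, 3 and 4.5 points are added to DCR. At 30% it is 9, 8 and 7 points for medians of 8, 12 and 16 weeks.

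**7. Weight of one patient.** 100/14 = 7.1, 100/20 = 5.0 and 100/29 = 3.4 points.

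**The case against.** The strongest reply is that the larger error belongs to an optional route. Four scans are the default, at which it essentially vanishes, and the two-scan analysis requires the responder criterion to be settled with certainty. This stands and limits the finding to the two-scan cut-off or lock. It does not remove it, because the plan permits both.

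Second, the no-responder range is an upper scenario. This also stands, and step 4 gives the lower range. The 20-point end further requires 20 patients within 4 months.

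Third, a reader might infer from the eye toxicity that delays will be frequent and the late-progression error large. The documents do not support that. None of the 10 first-in-human patients given prophylaxis had an eye disorder leading to dose modification (Protocol 4.1.2), and prophylaxis is mandatory here. The 29.4% reported at 90 mg/m² D1D8 is per patient, whereas 30% per two-cycle block means 1 − 0.7² = 51% of patients delayed by the second scan. Protocol 10.1.4 also anchors scans to first administration rather than to cycles.

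Fourth, a reader might infer that the rule could favour the more toxic dose. Dose selection uses ORR and safety (Protocol 6.3; SAP 1.1), and DCR has no test or decision attached, so this does not follow.

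Fifth, the Kaplan-Meier progression-free probabilities at 3 months (SAP 2.4.4.2.4 and 2.4.4.2.5) censor ongoing Day 84 patients instead of failing them. That softens the consequence but does not correct the reported DCR. Finally, ending SD at the progression date is a common convention, which is a reason to retain it as a sensitivity analysis.

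**Conclusion.** The concern holds in a limited form and is minor. The misordering in step 2 follows from the SAP text for any month longer than 28 days. The understatement of DCR matters only if data are cut or locked after two scans: about 6 to 20 points without responders, or about 3 to 11 points with the first-in-human responder share. Both ranges assume exponential progression with a median of 8 to 12 weeks and 4 to 12 months' accrual of 20 patients. At four scans it is essentially 0. The opposite error is 0 without delays and about 1 to 5 points if 5% to 15% of two-cycle blocks are delayed. The frequency of deaths after Day 91 without a second scan cannot be estimated from the documents. ORR, the 7/29 test and dose selection are unaffected.

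**What to change.** In SAP 2.1.3.2.2 and Protocol 9.2.1:

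- Count the SD component of DCR as met by a valid assessment of SD or better, without prior progression, at the scheduled week-12 scan or later, with a stated window. One week is an example, which would admit scans from Day 77; the plan has no such window now.
- Use the same wording, at least, in both documents.
- Report as a sensitivity analysis the DCR with SD duration run to the progression or death date as now written.

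Under the new rule the Day 84 record passes, and the two records with SD only at Day 42 fail.

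The cost is a wording change in two documents and one extra table, using scans already planned. The drawback is that the threshold becomes 12 weeks instead of 3 months, so any comparison with the first-in-human DCR needs a footnote.

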In the presence of evidence suggestive of progression, such as increasing liver enzymes, declining performance status, weight loss, or increasing pain, every reasonable effort should be made to document the nature of progressive disease by appropriate imaging studies. The Investigator may remove a patient from the study treatment either for clinical progression, when it is not possible to obtain an imaging study, or for any other reason determined as in the best interest of the patient to do so; however, the rationale for this decision must be recorded in the patient's medical chart and in the eCRF.

Clear evidence of response and of progression must be documented in the patient's medical record and this data will be recorded in the eCRF.

The Investigator at the site will be responsible for the assessment and collection of the radiographic information in compliance with the schedule of evaluations presented in this protocol.

A quick reference guide to RECIST 1.1 is included in [Appendix A](#).

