- **Blood sampling for PK:** as specified in PK/immunogenicity flow chart (see [Section 1.4](#)).
- **Blood sampling for ATA:** as specified in PK/immunogenicity flow chart (see [Section 1.4](#)).
- **Tumor assessment** every 6 weeks after first study treatment administration: (abdominal/chest) CT Scan or MRI, and all other exams as clinically indicated (eg, brain CT scan or MRI in case of clinical suspicion of central nervous system involvement) to assess all TARGET or NON TARGET lesions. To ensure comparability, the imaging should be performed using identical techniques throughout the study period (ie, scans performed immediately following bolus contrast administration using a standard volume of contrast, the identical contrast agent, and preferably the same scanner).

Confirmation of objective responses will be performed by repeat tumor imaging (CT scan, MRI) at least 4 weeks after the first radiological documentation of response (see [Section 9.1.2](#)).
- **Other investigations** if clinically indicated.

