10.1.6 Follow-up period

During the follow-up period, SAEs (regardless of relationship with study treatment) and IMP-related AEs ongoing at the end of study treatment, as well as new IMP-related AEs/SAEs, will be followed until resolution or stabilization, where stabilization is defined as an event ongoing without any change for at least 3 months. During the follow up period, patients will be followed up every 6 weeks (± 1 week) until death, study cut-off, or withdrawal of patient's consent, whichever comes first. For patients who discontinue study treatment prior to documented disease progression, a tumor assessment will be performed every 6 weeks. Date of disease progression and further anticancer treatment will be collected at the follow-up visit.

The following procedures will be performed/assessed:

- **ECOG PS and body weight.**
- **Tumor assessment** (if applicable, ie, if disease progression has not yet been documented).
- **Post-study treatments:** if used to treat new or unresolved treatment-related AEs.
- **Adverse events:** any treatment-related AEs and all SAEs ongoing at the end of study treatment, and new treatment-related AEs or SAEs will be recorded until recovery, or until the event has been stabilized.
- **Further anticancer therapy:** in case a patient discontinues study treatment due to a reason other than progressive disease, further antitumor therapy will not be initiated before progression is documented.

- [REDACTED]
- **Blood sampling for ATA:** as specified in PK/immunogenicity flow chart (see [Section 1.4](#)).

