10.1.7 Post study cut-off date

- Patients still on study treatment at the second cut-off date can continue study treatment, if clinical benefit is observed, until disease progression, unacceptable toxicity, or the patient refuses further study treatment, and will continue to undergo all assessments as per the study flow chart.
- Patients without documented disease progression but not on treatment at the second cut-off date will be followed for any ongoing AEs. In addition, imaging to document disease progression and survival status will be collected (every 6 weeks) for 6 months after the cut-off date.

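### The SAP replaces the protocol's 95% intervals with 80% for all four secondary efficacy endpoints and widens the TTP event, recording neither change; a lesser item is the unclear end date of stable disease after new anticancer therapy

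*SAP*

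**What the plan says.** **Interval level.** Protocol Section 11.4.4.2 gives exact 95% intervals for DCR and 95% intervals for median duration of response (DOR), PFS and TTP; the protocol synopsis repeats 95% for DCR. SAP Sections 2.4.4.2.1 (DCR), 2.4.4.2.2 (DOR), 2.4.4.2.4 (TTP) and 2.4.4.2.5 (PFS) all give 80%.

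**TTP event.** The protocol synopsis and Section 9.2.1 count only radiologically documented progression. SAP Section 2.1.3.2.3 also counts death from disease progression before any new anticancer therapy.

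**Record of changes.** SAP Section 1.6, which is reserved for statistical modifications made in the SAP, is marked not applicable.

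**End of stable disease (SD).** SAP Section 2.1.3.2.2 has three bullets:

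- The first ends SD at progression, death or the "date of last valid tumour assessment before the initiation of any post-treatment anti-cancer therapy".
- The second covers new therapy given before radiologic progression or death: "the duration of response will be calculated until the date of the last valid response assessment without evidence of progression". It names response although the section concerns SD.
- The third covers new therapy given without radiologic progression or death: "the duration of stable disease will be calculated until the date of initiation of the post-treatment anti-cancer therapy".

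SAP Sections 2.1.3.2.1 (DOR) and 2.1.3.2.3 (TTP) contain the same before/without pair. The SD threshold is *at least* 3 months in the protocol synopsis and the SAP, but *more than* 3 months in Protocol Section 9.2.1. Neither document converts 3 months to days.

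**The concern.** The interval level and the TTP event affect what is reported for every patient. A reader who takes the protocol as the specification expects 95% intervals and a radiologic TTP. The SAP delivers narrower intervals and a different event, and its own change section says that nothing was altered.

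The SD rule is narrower. The first and third bullets give different dates for one situation, and no text says which takes priority. If the second and third bullets are read as special cases of the first, each patient has a single date. That date then depends on whether progression or death is recorded after the new therapy. This sits badly with SAP Section 2.1.3.1: "Tumor assessments after the initiation of post-treatment anti-cancer therapy will be excluded from the determination of Best Overall Response in a patient". The SAP itself calls the SD duration critical for deciding who counts in DCR.

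The situation can arise. Protocol Section 10.1.6 says that "further antitumor therapy will not be initiated before progression is documented", but only for patients who stop treatment for a reason other than progressive disease. Protocol Section 9.1.2 lets the investigator remove a patient "either for clinical progression, when it is not possible to obtain an imaging study". Such a patient may start new therapy with no documented progression, and the third bullet would then credit SD time after the clinical progression.

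**Working it through.** The plan states no figure of its own on this point, so there is none to reproduce.

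**1. Interval level.** Exact (Clopper-Pearson) limits for x of n at confidence 1−a are the a/2 quantile of Beta(x, n−x+1) and the 1−a/2 quantile of Beta(x+1, n−x). As an illustration, take x near the 36.8% DCR that Protocol Section 4.2 reports for breast cancer patients in the first-in-human study: 0.368 × 29 = 10.7, so 11; 0.368 × 20 = 7.4, so 7.

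| x/n | 80% interval | 95% interval | Widths (points) | Ratio |
|---|---|---|---|---|
| 11/29 | 25.7–51.5% | 20.7–57.7% | 25.8 and 37.0 | 0.70 |
| 7/20 | 20.7–51.8% | 15.4–59.2% | 31.1 and 43.8 | 0.71 |

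The SAP's DCR intervals are therefore about 30% narrower than those the protocol specifies. The median DOR, PFS and TTP intervals also narrow, by an amount that depends on the data.

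**2. TTP event.** A patient who dies of disease progression with no radiologic progression and no new therapy has an event under the SAP and none under the protocol's definition. How many such patients there will be cannot be derived from the documents.

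**3. SD end date.** Scans are due "every 6 weeks after first study treatment administration", so nominally on days 42, 84 and 126. Assume 3 months is 90 to 92 days. Take a last valid SD scan on day 84, new therapy on day 95, and no radiologic progression or death.

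- First bullet: 84 days (84/30.4375 = 2.76 months), not disease control.
- Third bullet: 95 days (95/30.4375 = 3.12 months), disease control.
- Special-case reading: 84 days if progression or death is recorded after the new therapy, 95 days if not, with identical data up to day 95.

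With last valid scan L, threshold T and therapy start S, status differs only if L < T ≤ S (with *at least*). No later valid scan may precede S.

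**4. The end-of-treatment scan.** Protocol Section 10.1.5 schedules a tumor assessment 25 to 35 days after the last dose. If the last infusion is Cycle 4 Day 8 (63 + 7 = 70 days after the first), that is day 95 to day 105. A valid non-progression scan on or after the threshold and before new therapy gives disease control under either rule. A progression scan before new therapy takes the patient out of the third bullet. The gap remains when the scan is not done or falls after new therapy starts. Footnote r in Protocol Section 1.3 waives it if it was already done at the last cycle.

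**5. Size per patient.** 1/29 = 3.4 points, 1/20 = 5.0, 1/14 = 7.1. For example, 10/29 = 34.5% and 11/29 = 37.9%.

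**6. DOR and TTP.** With scans on schedule, progression is dated on scan days. Moving a censoring date within one 42-day gap crosses no progression time, so the Kaplan-Meier estimates barely move. Deaths and off-schedule or missed scans are the exceptions.

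**The case against.** **The SAP may refine the protocol.** Protocol Section 11 leaves accurate definitions and detailed specifications to the SAP, so a sharper TTP event is partly foreseen. The 80% level also matches the interval both documents give for the primary response rate and the one-sided 10% test. Table 1 in SAP Section 1.5 concerns protocol amendments, so silence there proves little. All of this stands. It does not explain why Section 1.6 is marked not applicable when a specified level was replaced for four endpoints.

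**The SD bullets need not contradict each other.** A reader might infer that the SAP assigns two dates to one patient. A general rule followed by conditional ones is usually read as rule and special cases, and then each patient has one date. That objection succeeds against a flat contradiction. The dependence on events after new therapy remains.

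**Frequency.** For a day-84 last scan and therapy starting on days 85 to 126, the two rules differ on 35 to 37 of 42 start days (thresholds 92 to 90, *at least*). A reader might take this as a measure of how often status changes. It is not: it counts calendar days rather than probabilities, and it ignores the end-of-treatment scan.

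**Later change of status.** A reader might infer that a reported DCR could shift after the second cut-off, because "imaging to document disease progression and survival status will be collected (every 6 weeks) for 6 months after the cut-off date". SAP Section 4 ties database lock to completed tumor assessments, and no later DCR re-analysis is specified. The documents do not support that inference.

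**Conclusion.** The mismatch in interval level is established on the text and covers all four secondary efficacy endpoints. In the illustration it narrows the DCR interval by about 30%. The TTP event also differs between the documents, by an unknown number of patients. Neither change is recorded in SAP Section 1.6.

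The SD end date is a lesser item. It changes DCR status only when the last valid SD scan falls before the threshold, no later valid scan (including the end-of-treatment scan) precedes new therapy, and therapy starts on or after the threshold. The number of such patients is unknown and probably very small. The day counts rest on the assumption that 3 months is 90 to 92 days.

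A reader should not infer any effect on the primary result. The response-rate test uses none of these rules, PFS is touched only through its interval level, and the secondary endpoints are descriptive with no decision attached to them.

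**What to change.** - Report the protocol's 95% intervals for DCR, DOR, PFS and TTP; 80% intervals may be added. Use one TTP event definition in both documents. Alternatively, list each retained change with its reason in SAP Section 1.6.
- In SAP Section 2.1.3.2.2, delete the third bullet and end SD at the last valid assessment before new therapy for every such patient. Correct the second bullet to refer to duration of stable disease. Either date applied consistently would remove the ambiguity. The last assessment is preferable because the first two bullets already use it and it does not depend on later events.
- For consistency, use the same last-assessment censoring in SAP Sections 2.1.3.2.1 and 2.1.3.2.3; the numerical effect is small.
- Define 3 months in days and use either *at least* or *more than* throughout.

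The cost is some SAP wording and a few lines of code. Secondary intervals become wider and credited durations slightly shorter. Censoring at new therapy can still be informative; the change only makes the date unambiguous.
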